8.2. Columbia-Suicide Severity Rating Scale (C-SSRS)

For suicidal ideation, the pre-treatment reference period is the lifetime history, current history and baseline (for further detail refer to the IDSL documentation). For suicidal behavior, the pre-treatment reference period is the lifetime history and baseline (note: suicidal behavior is not re-assessed for the current history time period).

[figure not shown]
Suicidal ideation and suicidal behavior will be considered as distinct categories and assessed independently of each other. Treatment emergence will be assessed for the on treatment period and the on-study period.

Suicidal ideation will be assessed using responses to C-SSRS ideation questions (categories 1 to 5) only. Suicidal behavior will be assessed using responses to C-SSRS behavior questions (categories 6 to 10) only.

- **Treatment emergent suicidal ideation** will be assessed using the maximum ideation score pre-treatment, compared to the maximum ideation score post-treatment (Year 1 or Year 2 as appropriate). If the maximum ideation score worsens relative to the pre-treatment reference period then this will be considered a treatment emergent suicidal ideation. This is derived from responses to suicidal ideation questions (categories 1 to 5).
- **Treatment emergent suicidal behavior** will be assessed using the maximum behavior score pre-treatment, compared to the maximum behavior score post-treatment (Year 1 or Year 2 as appropriate). If the maximum behavior score worsens relative to the pre-treatment reference period then this will be considered a treatment emergent suicidal behavior. This is derived from responses to suicidal behavior questions (categories 6 to 10).
- **Treatment emergent suicidal ideation or behavior** will be defined as a subject having a treatment emergent suicidal ideation (as defined above) and/or a treatment emergent suicidal behavior (as defined above).

[figure not shown]
Suicidal Ideation (categories):

CCI - This section contained Clinical Outcome Assessment data collection questionnaires or indices, which are protected by third party copyright laws and therefore have been excluded.

Suicidal Behavior (categories):

CCI - This section contained Clinical Outcome Assessment data collection questionnaires or indices, which are protected by third party copyright laws and therefore have been excluded.

A subject must have at least one pre-treatment C-SSRS assessment (screening and/or baseline) and at least one on treatment C-SSRS assessment (post-baseline) to be included in any assessment of treatment emergent.

If a “yes” response is given to any suicidal behavior or a “yes” response is given to suicidal ideation questions 3, 4 or 5 on the C-SSRS, the investigator will be prompted to complete the Possible Suicidality Related Questionnaire (PSRQ).

All C-SSRS tables will be presented for subjects whilst on study.

8.2.1. C-SSRS Suicidal Ideation or Behaviour on Study [T13.52, T23.45].

The number and percentage of subjects with each category of suicidal ideation or behavior during treatment (starting after Day 1 assessment) will be presented for Year 1, and Year 2. For suicidal ideation, the maximum ideation score (1-5) at any time during the relevant period will be presented. For suicidal behavior, all behaviors (6-10) present at any time during the relevant period will be presented. This will be regardless of whether the subject had pre-treatment history (up to and including baseline). The categories of suicidal ideation and behavior are presented in increasing order of severity from 1 to 5, and 6-10 respectively.

8.2.2. C-SSRS Suicidal Ideation or Behavior Relative to Pre-Treatment [T13.53, T23.46].

The number and percentage of subjects with treatment-emergent suicidal ideation or behavior -post-baseline will be presented for Year 1 and Year 2.

A subject must have at least one pre-treatment C-SSRS assessment (screening and/or baseline) and at least one Year 1 or Year 2 (respectively) C-SSRS assessment to be included in this display.

A subject may have treatment emergent suicidal ideation and/or behavior.

The following categories will be presented:

- The number (%) of subjects with any treatment emergent suicidal ideation (1-5)
 - The number (%) of subjects with any treatment emergent more severe suicidal ideation (4-5)
- The number (%) of subjects with any treatment emergent suicidal behavior (6-10)
- The number (%) of subjects with any treatment emergent suicidal ideation (1-5) or suicidal behavior (6-10)

Note: treatment emergent suicidality can only be assessed in subjects with a pre-treatment maximum ideation score of 4 or lower (as subjects with a pre-treatment ideation score of 5 have no potential to worsen on the 1-5 ideation scale)

8.2.3. C-SSRS Shift Changes in Categories from Pre-Treatment to On-Study [T13.54, T23.47].

A summary of the shift from maximum pre-treatment C-SSRS category to maximum category during Year 1 and Year 2 separately will be produced by treatment group.

The pre-treatment period for ideation is based on the lifetime, current and baseline history. For behavior, it is based on the lifetime and baseline history. A subject must have at least one pre-treatment assessment and at least one assessment during Year 1 or Year 2 (respectively) in order to be included in these displays.

The table will display the number and percentage of subjects within the specific shift categories: No suicidal ideation or behavior, suicidal ideation, and suicidal behavior.

Each subject will appear in the table only once. For the purposes of this table only, a subject with both suicidal ideation and suicidal behavior in any period (pre-treatment/on-treatment/on-study) will appear in the category of suicidal behavior only.

8.2.4. C-SSRS Shift Changes in Categories from Year 1 to Year 2 [T23.48].

A summary of the shift from last Year 1 C-SSRS assessment to maximum Year 2 C-SSRS assessment will be produced by treatment group.

The last Year 1 is based on the current assessment. A subject must have at least one Year 1 assessment, and at least one assessment during Year 2 in order to be included in these displays.

The table will display the number and percentage of subjects within the specific shift categories: No suicidal ideation or behavior, suicidal ideation, and suicidal behavior.

Each subject will appear in the table only once. For the purposes of this table only, a subject with both suicidal ideation and suicidal behavior in any period (pre-treatment/on-treatment/on-study) will appear in the category of suicidal behavior only.

8.3. Clinical Laboratory Analyses

Laboratory evaluations including the analyses of Chemistry laboratory tests, Hematology laboratory tests, Urinalysis, and liver function tests will be based on GSK Core Data Standards.

For laboratory analyses analytes will be analyzed and summaries and analyses will be performed based on the observed data. No imputation will be done for missing data. Baseline is defined as described in Section 5.3. See Protocol Appendix 9 for a list of laboratory parameters. Laboratory toxicity grades will be assigned based on DMID (see Section 15.8 Appendix 8: Laboratory Parameters and Toxicity Grades) by the laboratory,

with the exception of Lymphopenia (as there is no DMID grade). Lymphopenia will be graded as per CTCAE v4.03.

Calcium, will be presented as hypercalcaemia and hypocalcaemia separately (with each subject appearing in both categories) and similarly for sodium (hypernatremia, hyponatremia), potassium (hyperkalemia, hypokalemia), and glucose (hyperglycemia, hypoglycemia).

Listings will be generated for all laboratory results and for Grade 3 or Grade 4 laboratory toxicity results [L13.13 – L13.24, L23.14 - L23.26].

If a numeric laboratory value, has a non-detectable level reported in the database, then typically the numeric value is missing, and a character value starting with '<x' or '>x' is present. A numeric value will be derived using the number of decimal places in the observed character values i.e.

- 2 Decimal Places = '< x ' becomes $x - 0.01$
- 1 Decimal Place = '> x' becomes $x + 0.1$
- 0 Decimal Places = '< x' becomes $x - 1$

8.3.1. Laboratory Descriptive Statistics by Visit

Descriptive statistics for each analyte will be displayed for each visit for both the Year 1 and Year 1&2 reporting separately. The tables will display the mean value, standard deviation, median, 25th and 75th percentiles, minimum and maximum. No statistical tests will be performed [T13.55, T13.59, T13.63, T13.67, T13.74, T23.49, T23.53, T23.57, T23.61, T23.68].

A line graph will be produced for each analyte which displays the mean value (\pm SE) by visit and treatment group for both Year 1 and Year 1&2 separately [F13.01-F13.05, F23.01-F23.05].

8.3.2. Laboratory Toxicity \geq 2 Grade Shift Post-Baseline

Toxicity grade shifts from baseline of \geq 2 grades will be summarized during treatment for each laboratory parameter within each laboratory category (hematology, liver function, electrolytes, other chemistries, urinalysis and immunoglobulins) for Year 1 and Year 1&2 separately. The table will display the number and percentage of subjects with at least one \geq 2 grade shift as well as the specific shift categories: Grade 0 to 2, Grade 0 to 3, Grade 0 to 4, Grade 1 to 3, Grade 1 to 4 and Grade 2 to 4 [T13.57, T13.61, T13.65, T13.69, T13.72, T13.76, T23.51, T23.55, T23.59, T23.63, T23.66, T23.70].

8.3.3. Laboratory Reference Range Shifts from Baseline by Visit

For laboratory tests without toxicity grades, shifts relative to the normal range will be summarized for each analyte as shifts 'to low' and shifts 'to normal/high.' For the 'to low' category the percentage of subjects with at least one low post-baseline value relative

to the baseline will be displayed using the categories: remained low and normal/high to low. For the 'to normal/high' category the percentage of subjects with at least one normal/high post-baseline value relative to baseline will be displayed using the categories: remained normal/high and low to normal/high. No statistical tests will be performed. This analysis will be performed for Year 1 and Year 1&2 separately [T13.58, T13.62, T13.66, T13.70, T13.73, T23.52, T23.56, T23.60, T23.64, T23.67].

A laboratory value that is above the testing laboratory's normal range will be considered a high abnormal laboratory value. A laboratory value that is below the testing laboratory's normal range will be considered a low abnormal value.

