10.4.2. Safety Analyses

All safety analyses will be performed on the ITT Population.

Endpoint	Statistical Analysis Methods
Secondary	Descriptive statistics will be used to summarize AEs, SAEs, AEs of special interest (AESI), changes in laboratory parameters, and immunogenicity (both antibelimumab and anti-rituximab antibodies will be assessed). The frequency of laboratory abnormalities will be tabulated by treatment group. The frequency of AEs will be tabulated by MedDRA system organ class (SOC) and preferred term and compared between treatment arms.

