- A specialist or hepatology consultation is recommended

For All other criteria:

- Repeat liver chemistries (include ALT, AST, alkaline phosphatase, bilirubin) and perform liver event follow up assessments within 24-72 hrs
- Monitor participants weekly until liver chemistries resolve, stabilize or return to within baseline

bilirubin≥2xULN

- Obtain complete blood count with differential to assess eosinophilia
- Record the appearance or worsening of clinical symptoms of liver injury, or hypersensitivity, on the AE report form
- Record use of concomitant medications on the concomitant medications report form including acetaminophen, herbal remedies, other over the counter medications.
- Record alcohol use on the liver event alcohol intake case report form (CRF) page

For bilirubin or INR criteria:

- Anti-nuclear antibody, anti-smooth muscle antibody, Type 1 anti-liver kidney microsomal antibodies, and quantitative total immunoglobulin G (IgG) or gamma globulins.
- Serum acetaminophen adduct high performance liquid chromatography (HPLC) assay (quantifies potential acetaminophen contribution to liver injury in participants with definite or likely acetaminophen use in the preceding week [James, 2009]). NOTE: not required in China
- Liver imaging (ultrasound, magnetic resonance, or computerised tomography) and /or liver biopsy to evaluate liver disease: complete Liver Imaging and/or Liver Biopsy CRF forms.
- Serum bilirubin fractionation should be performed if testing is available. If serum bilirubin fractionation is not immediately available, discontinue study treatment for that participant if ALT ≥ 3xULN and bilirubin ≥ 2xULN. Additionally, if serum bilirubin fractionation testing is unavailable, record presence of detectable urinary bilirubin on dipstick, indicating direct bilirubin elevations and suggesting liver injury.
- All events of ALT ≥ 3xULN and bilirubin ≥ 2xULN (>35% direct bilirubin) or ALT ≥ 3xULN and INR>1.5, if INR
 measured which may indicate severe liver injury (possible 'Hy's Law'), must be reported as an SAE (excluding
 studies of hepatic impairment or cirrhosis); INR measurement is not required and the threshold value stated
 will not apply to participants receiving anticoagulants
- 3. New or worsening symptoms believed to be related to liver injury (such as fatigue, nausea, vomiting, right upper quadrant pain or tenderness, or jaundice) or believed to be related to hypersensitivity (such as fever, rash or eosinophilia)

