15.8. Appendix 8: Laboratory Parameters and Toxicity Grades

| Laboratory Assessments | Parameters | | | |
|---------------------------------|---|---|--|--|
| Hematology | Platelet Count | RBC Indices: MCV MCH MPV MCHC %Reticulocytes | | WBC count with Differential: Neutrophils Lymphocytes Monocytes Eosinophils Basophils |
| | RBC Count | | | |
| | RDW | | | |
| | Hemoglobin | | | |
| | Hematocrit | | | |
| | Activated partial thromoplastin time | | | |
| | Prothrombin Time | | | |
| Clinical Chemistry ¹ | BUN | Potassium | Aspartate Aminotransferase (AST)/ Serum Glutamic-Oxaloacetic Transaminase (SGOT) | Total and direct bilirubin |
| | Creatinine | Sodium | Alanine Aminotransferase (ALT)/ Serum Glutamic-Pyruvic Transaminase (SGPT) | Total Protein |
| | Glucose – Nonfasting | Calcium (corrected) | Alkaline phosphatase | eGRF |
| Routine Urinalysis | 
 • Standard Urinalysis Macro and Urinalysis Micro (microscopic examination if blood or protein is abnormal) • Specific gravity • pH, Glucose, Protein, Blood, Ketones, Occult Blood, Bilirubin, Nitrite, Leukocyte Esterase by dipstick • Spot Urine (protein:creatinine ratio) | | | |
| Immunoglobulins | 
 • Serum isotypes: IgG, IgM, IgA | | | |
| Autoantibodies | 
 • ANA titer • Anti-dsDNA • aCL • Beta-2-glycoprotein • Lupus anticoagulant • Extractable nuclear antigens (ENAs) | | | |

| Laboratory Assessments | Parameters |
|--------------------------|--|
| Serum Complement | 
 • Complement C3 • Complement C4 |
| Urine Drug Screen | 
 • Amphetamines, Barbiturates, Benzodiazepines, Cocaine Metabolites, Marijuana Metabolites, Methadone, Opiates, Phencyclidine, Propoxyphene, Ethanol |
| Genetics | 
 • Blood sample collection |
| Belimumab PK | 
 • Blood sample collection |
| Rituximab PK | 
 • Blood sample collection |
| RNA Interferon Signature | 
 • Blood sample collection |
| PBMC | 
 • Blood sample collection |
| Immunogenicity | 
 • Blood sample collection |
| B Cell Subset | 
 • Blood sample collection |
| B-Cell Receptor | 
 • Blood sample collection |

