Adverse Event and Laboratory Value Severity Grade Tables (continued)

| CHEMISTRIES | GRADE 1 MILD | GRADE 2 MODERATE | GRADE 3 SEVERE | GRADE 4 POTENTIALLY LIFE- THREATENING |
|--|-------------------------|-----------------------------|---------------------------|--|
| Sodium | | | | |
| Hyponatremia | 130-135 meq/L | 123-129 meq/L | 116-122 meq/L | < 116 meq/L |
| Hypernatremia | 146-150 meq/L | 151-157 meq/L | 158-165 meq/L | > 165 meq/L |
| Potassium | | | | |
| Hypokalemia | 3.0-3.4 meq/L | 2.5-2.9 meq/L | 2.0-2.4 meq/L | < 2.0 meq/L |
| Hyperkalemia | 5.6-6.0 meq/L | 6.1-6.5 meq/L | 6.6-7.0 meq/L | > 7.0 meq/L |
| Phosphate | | | | |
| Hypophosphatemia | 2.0-2.4 mg/dL | 1.5-1.9 mg/dL | 1.0-1.4 mg/dL | < 1.0 mg/dL |
| Calcium- (Corrected For Albumin) | | | | |
| Hypocalcemia | 7.8-8.4 mg/dL | 7.0-7.7 mg/dL | 6.1-6.9 mg/dL | < 6.1 mg/dL |
| Hypercalcemia | 10.6-11.5 mg/dL | 11.6-12.5 mg/dL | 12.6-13.5 mg/dL | >13.5 mg/dL |
| Magnesium | | | | |
| Hypomagnesemia | 1.2-1.4 meq/L | 0.9-1.1 meq/L | 0.6-0.8 meq/L | < 0.6 meq/L |
| Albumin | | | | |
| Hypoalbuminemia | 3.00-3.49 g/dL | 2.50-2.99 g/dL | 2.00-2.49 g/dL | < 2.00 g/dL |
| Bilirubin (Total) | | | | |
| Hyperbilirubinemia (Total) | > 1.0-1.5 x ULN | > 1.5-2.5 x ULN | > 2.5-5 x ULN | > 5 x ULN |
| Glucose | | | | |
| Hypoglycemia | 55-64 mg/dL | 40-54 mg/dL | 30-39 mg/dL | < 30 mg/dL |
| Hyperglycemia (nonfasting & no prior diabetes) | 116-160 mg/dL | 161-250 mg/dL | 251-500 mg/dL | > 500 mg/dL |
| Triglycerides | 151-399 mg/dL | 400-750 mg/dL | 751-1200 mg/dL | > 1200 mg/dL |
| Creatinine | > 1.0-1.5 x ULN | > 1.5-3.0 x ULN | > 3.0-6.0 x ULN | > 6.0 x ULN |
| Uric Acid | | | | |
| Hyperuricemia | 7.5-10.0 mg/dL | 10.1-12.0 mg/dL | 12.1-15.0 mg/dL | > 15.0 mg/dL |
| Liver Transferases (AST, ALT, and GGT) | 1.25-2.5 x ULN | > 2.5-5.0 x ULN | > 5.0-10.0 x ULN | > 10.0 x ULN |
| Alkaline Phosphatase | 1.25-2.5 x ULN | > 2.5-5.0 x ULN | > 5.0-10.0 x ULN | > 10.0 x ULN |
| Pancreatic Enzymes | | | | |
| Amylase | > 1.0-1.5 x ULN | > 1.5-2.0 x ULN | > 2.0-5.0 x ULN | > 5.0 x ULN |
| Pancreatic amylase | > 1.0-1.5 x ULN | > 1.5-2.0 x ULN | > 2.0-5.0 x ULN | > 5.0 x ULN |
| Lipase | > 1.0-1.5 x ULN | > 1.5-2.0 x ULN | > 2.0-5.0 x ULN | > 5.0 x ULN |
| Hypoglobulinemia (IgG)* | 550-700 mg/dL | 400-549 mg/dL | 250-399 mg/dL | < 250 mg/dL |
| | | | | (continued) |

Modified from (DMID) Adult Toxicity Tables, 2001

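### The reference-range shift tables for ungraded laboratory tests have no to-high category, so the number of participants rising above the upper limit of normal is not tabulated by arm

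*SAP*

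**What the plan says.** SAP 8.3.3 sets the rule: "For laboratory tests without toxicity grades, shifts relative to the normal range will be summarized for each analyte as shifts 'to low' and shifts 'to". The second label, cut short in the quote, is *to normal/high*. Under *to low* the cells are *remained low* and *normal/high to low*. Under the other label, the percentage of participants "with at least one normal/high post-baseline value relative to baseline will be displayed using the categories: remained normal/high and low to normal/high". The section then states that "A laboratory value that is above the testing laboratory's normal range will be considered a high abnormal laboratory value", but none of its cells uses that definition. No statistical test is planned.

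Protocol 10.4.2 makes a commitment that is not limited to low values: "The frequency of laboratory abnormalities will be tabulated by treatment group". SAP 15.6.1 adds a general convention for safety parameters: a participant with both a High and a Low value after baseline is counted in both categories of the any-visit row of the related summary tables.

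For each analyte at each visit, SAP 8.3.1 also plans descriptive statistics: "The tables will display the mean value, standard deviation, median, 25th and 75th percentiles, minimum and maximum". SAP 8.3 plans listings of all results. The worst-grade tables (8.3.5) and the tables of shifts of two grades or more (8.3.2) depend on a toxicity grade.

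**The concern.** The two-class split suits analytes for which only a low value is of interest. The SAP uses it that way for immunoglobulins (8.3.4) and complement (10.2). For BUN, direct bilirubin and eosinophils the direction of interest is upward, and the split removes it.

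The protocol itself looks upward for two of these. Direct bilirubin above 35% is part of a liver stopping criterion in Appendix 5. The follow-up list in the same appendix says "Obtain complete blood count with differential to assess eosinophilia", and Appendix 6 treats eosinophilia as a marker of hypersensitivity when restart is considered. Those are instructions for individual cases, not for summary tables, but they show which direction matters.

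What is at stake is a comparison of arms: whether more participants on the combination than on control moved above the normal range on a test that has no grade. These shift tables are the only planned categorical laboratory summaries for such tests.

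**Working it through.** The point concerns table layout, and the plan gives no figure to reproduce. The check sets the rule beside every possible transition and then beside the other planned displays.

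**Step 1. Are the example tests ungraded?** SAP Appendix 8 (15.8) lists BUN, "Total and direct bilirubin" and eosinophils as study analytes. The grade tables in 15.8.1 have no row for BUN or eosinophils. Their bilirubin row is for the total only ("Hyperbilirubinemia (Total", closing bracket omitted). All three tests therefore fall under 8.3.3.

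**Step 2. Map the nine transitions to the four cells of 8.3.3.**

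| Baseline | Post-baseline low | Post-baseline normal | Post-baseline high |
|---|---|---|---|
| Low | remained low | low to normal/high | low to normal/high |
| Normal | normal/high to low | remained normal/high | remained normal/high |
| High | normal/high to low | remained normal/high | remained normal/high |

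In every row the last two columns are identical. All 3 transitions that end high share a cell with one that ends normal. Normal-to-high prints as *remained normal/high*, and low-to-high prints as *low to normal/high*.

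**Step 3. Illustration with assumed numbers.** Take the target sizes, 140 in Arm B and 70 in Arm A. Suppose everyone is normal at baseline, nobody goes low, and 10 in Arm B and none in Arm A go above the limit on BUN.

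- Layout of 8.3.3, *remained normal/high*: 140/140 = 100% and 70/70 = 100%.
- Layout with a *to high* cell: 10/140 = 7.1% and 0/70 = 0%.

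Under these assumptions the first line is the same whether 0% or 100% of an arm goes high.

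**Step 4. Does another planned table supply the count?**

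- Worst-grade and two-grade-shift tables: not for a test without a grade.
- By-visit statistics: quartiles and the maximum show that some values are high, but not how many participants exceeded the limit.
- Adverse event tables: incidence by arm, but only for changes judged clinically relevant and recorded as events (protocol 9.9.4 and Appendix 7).
- Listings: individual values, with no incidence by arm.

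None gives the number above the upper limit.

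**Step 5. Which tables are affected?** SAP 8.3.3 names T13.58, T13.62, T13.66, T13.70 and T13.73 for Year 1. By their sequence, T13.66 is the electrolyte table. The electrolytes named in Appendix 8 are sodium, potassium and calcium, and 15.8.1 grades each in both directions, so no listed electrolyte is shown to be affected. For Year 1&2, the July 2021 addendum (2.1.7) does not list the ungraded shift tables (old T23.52, T23.56, T23.60, T23.64, T23.67). It keeps the graded tables and one immunoglobulin shift table.

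**The case against.** A reader might infer that renal, cholestatic or hypersensitivity harm would be hidden. The documents do not support that. Creatinine, total bilirubin, alkaline phosphatase and the transferases are graded, so worst-grade and two-grade-shift tables give their incidence by arm. ALT of at least 3 times the upper limit with bilirubin of at least 2 times the limit (more than 35% direct) must be reported as a serious adverse event. Systemic and hypersensitivity reactions are tabulated as events of special interest, and serious ones are adjudicated. For several ungraded tests, such as hematocrit and total protein, low is an obvious concern, and *to low* is tabulated.

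It is also fair to say that the layouts sit in separate safety shells (SAP 15.11.2) and that laboratory analyses follow the sponsor's data standards. Neither is in the documents. SAP 15.6.1 suggests that separate High counts may have been intended.

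The first argument stands as a limit on the size of the point. It does not supply the missing count, because a graded relative is a different analyte. The second leaves the intention open, but it does not cure the written rule: shells with a High column would contradict 8.3.3, and shells without one would leave the gap. Either way 8.3.3 and 15.6.1 have to be reconciled.

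**Conclusion.** The point holds for these tables and no further. As written, 8.3.3 merges every shift to an abnormally high value with values that end normal. For ungraded tests the incidence above the upper limit is therefore not tabulated by arm in any table the SAP describes. This leaves the commitment in protocol 10.4.2 unmet for high values of those tests and conflicts with the convention in 15.6.1.

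The size is modest. The named examples are three analytes, the tables are descriptive and untested, and no efficacy conclusion depends on them. The 7.1% against 0% in the illustration is assumed, not observed. The conclusion rests on the SAP text, since the shells cannot be seen, and on 15.8.1 being the complete set of grades applied.

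**What to change.** In SAP 8.3.3, classify baseline and post-baseline values as low, normal or high. Report *to low* and *to high* for each ungraded analyte, and count a participant with both in both, as 15.6.1 already provides. Keep the two-class split for immunoglobulins and complement. Align the shells with the revised text.

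Rerun whichever of the five Year 1 shift tables contain ungraded analytes. On the Appendix 8 list, the electrolyte table may need no change. The addendum lists no Year 1&2 versions, so the change applies there only if such a table is produced.

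The addendum was written after the first database lock and primary analyses, so this is a retrospective rerun as well as a text edit. It uses data already held, needs no new test and leaves the efficacy analyses untouched. The cost is a short amendment and the reprogramming of a few descriptive tables.
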